9.0 STUDY PROCEDURES

9.1 Provider Survey Study Procedures

During the study start-up period, clinic medical directors at 10-20 candidate sites will be asked to provide the study team with the number of HIV providers in their clinic and associated email addresses. The lead team will email all HIV providers a brief description of the survey and a website link that will redirect the provider computer to the Provider Survey Study. Once the link is activated, HIV providers will provide brief consent and complete a brief (10 minute) anonymous survey regarding their knowledge, attitudes and willingness to prescribe medication-assisted therapy for patients with opioid use disorders (methadone, buprenorphine, XR-NTX) or alcohol use disorders (disulfiram, acamprosate, XR-NTX), demographic, and practice characteristics. In collaboration with the DSC, the study team will track response rates and encourage medical directors to help in maximizing provider participation. Providers will be given a maximum of 4 weeks to complete the survey.

9.2 Pilot Study Procedures

Activity:	Screening/Enrollment	Detox/Induction	Active treatment
Duration:	1-4 weeks	0-4 weeks	16 weeks
	Total Duration:		17-24 weeks

9.2.1 Pre-screening

Individuals will be approached by study staff in HIV clinic settings or referred to study staff by HIV clinical care and outreach teams. Study staff will present a brief recruitment script to the individual and provide written information regarding XR-NTX. Individuals will provide verbal consent (determined by local IRB guidelines, and HIPAA authorization/Waiver as necessary) for pre-screening and will be asked to complete the Pre-Screening Interview. The Pre-Screening Interview will elicit information about the potential participant's demographics, use of antiretroviral therapy, drug use, and attitudes toward medication-assisted treatment of opioid and alcohol use disorders. The screening informed consent, HIPAA authorization (if necessary), and screening interview will take approximately 5, 5, and 10 minutes to complete, respectively.

9.2.2 Screening and Enrollment Procedures (1-4 weeks duration)

Once a person has completed the Pre-Screening Interview process and meets basic eligibility, they will either be asked to stay for the Screening Visit or scheduled to come back (based on staff and candidate's availability).

9.2.3 Informed Consent Process

Study procedures and the potential risks and benefits of participating in the trial will be explained by research staff. Staff will be available to answer questions about the consent form while participants are reviewing it. After signing the consent form, participants will be offered a copy of the form to keep for their records. The process will take approximately 20-30 minutes.

9.2.4 Locator Form

Participants will complete a locator information form which will be used to contact them to remind them of follow-up visits and to locate participants who cannot be found. When completing this form, participants provide their names, addresses, and telephone numbers as well as contact information for at least two other persons. Permission will also be requested to obtain locating information from additional agencies and publicly accessible databases or search engines including, but not limited to, Medicare/Medicaid and Social Security offices, department of motor vehicles, local jail logs, white pages, Facebook, etc. Locator information will be updated as needed during the study. The locator information form will take approximately 5-10 minutes to complete.

9.2.5 Medical Record Release Form

Participants will complete these forms throughout the study (as applicable) to grant permission to study staff to review inpatient, outpatient, mental health, and substance use treatment clinic records as needed. The purpose of medical record review at the end of study participation is to document information needed to evaluate secondary outcomes. Specifically, study staff will abstract medical record information to corroborate participants' self-report of information including, but not limited to the following: HIV viral load and CD4 count, liver enzymes, hepatitis B and C serologies, CBC, metabolic panel, INR, utilization of HIV primary care, utilization of HIV and addiction treatment services, and overdose events. Records review/abstraction will occur throughout the study (as needed) and up to 24 weeks post-randomization.

9.2.6 Collection of Biological Specimens

Study staff will collect blood and urine specimens at screening and baseline to confirm study eligibility and 0, 1, 4, 8, 12, and 16 weeks following treatment initiation to assess participant safety, and assess the pilot study secondary aim of change in HIV-1 RNA pcr and drug use. Baseline hepatitis B and C serologies drawn in the 90 days prior to consent may be abstracted from participant medical records, when available. Other baseline studies may be abstracted from medical records if drawn in the 30 days prior to consent. Some participating sites may require that copies of some or all lab results collected for study purposes be filed in participants' medical records.

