6.2 Duration of Study and Visit Schedule

The CHOICES pilot study will target enrolling no more than 50 participants over no more than

12 months at 2 HIV clinic sites. Each participant will be engaged in the overall study for approximately 17-24 weeks (Figure 9.2) as follows:

- Up to 4 weeks: Consent, screening, randomization.
- Up to 4 weeks: Detoxification and induction.

- 16 weeks: Active treatment with monthly study visits.

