8.2 Secondary Outcome Measures

1) HIV outcomes:

- a) HIV-1 RNA viral suppression (plasma HIV-1 RNA pcr < 200 copies/mL) at 16 weeks compared with screening (binary, laboratory assay).
- b) Change in CD4 count at 16 weeks following treatment initiation compared with screening (count; laboratory measurement).

2) Substance Use:

- a) Change in 30 day opioid abstinence (by Addiction Severity Index (ASI)-lite self-report, Time-Line Follow-Back (TLFB) and urine drug screen (UDS) confirmation) in the final 30 days of the 16 week trial compared to screening (binary; laboratory data and self-report).
- b) Change in past 30-day alcohol and other drug use by ASI-lite, TLFB and UDS at week 16 visit, compared to screening (binary; laboratory data and self-report).

3) Engagement in HIV Care:

- a) Change in the proportion of participants prescribed ART within 16 weeks following randomization, compared to baseline (binary; medical record abstraction).
- b) Proportion of participants taking 100% of prescribed ART doses in the past 3 days at 16 weeks for those prescribed ART at any point during the 16 week trial (proportion; self-reported ACTG adherence measure).
- c) Number of HIV primary care visits at 16 weeks (count, chart abstraction).

4) Participant safety:

- a) Change in liver enzymes between screening and week 16 visit (laboratory assay).
- b) Any fatal and non-fatal opioid overdose between screening and week 16 (binary; medical record abstraction and self-report).
- c) Change in Concise Health Risk Tracking score between screening and week 16 visit (continuous; self-report).
- d) Proportion of participants assigned to XR-NTX who develop precipitated opioid withdrawal.

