9.2.8 Randomization

We anticipate that the timing of randomization will be variable, but follow shortly after baseline assessments and final confirmation of eligibility. Participants will have up to 4 weeks following randomization to initiate his or her assigned treatment. Success in initiating assigned treatment will be tracked.

Participants will be randomized in a 1:1 fashion to either office-based XR-NTX or TAU using a permuted block design with randomly-sized blocks. Predominance of alcohol vs. opioid use disorder for a given participant will

likely be strongly correlated with primary and secondary outcomes, and this variable will be recorded upon randomization. The severity of opioid and alcohol use disorder will also likely be an important independent predictor of treatment retention and substance use (Sullivan, Rothenberg et al. 2006; Carpenter, Jiang et al. 2009; Brooks, Comer et al. 2010). Participants need not be abstinent from opioids or alcohol at the time of randomization.

The randomization procedure will be conducted in a centralized process through the Data and Statistical Center (DSC). Specifically, randomization schedules will be created by the study statistician for each site. The randomization schedules will be of a randomized-block nature to ensure relative equality of assignment across condition across the recruitment period and to prevent the potential for study staff guessing the next assignment which is heightened when a fixed block-size is used. After the baseline assessment is successfully completed, a designated study staff member will perform the randomization. Randomization for each participant is done over the Internet using the Enrollment Module in AdvantageEDC.

The DSC statistician will review the randomization data on a regular basis to ensure that the scheme is being implemented according to plan. If a participant drops out of the study at any point after randomization, the randomization slot will not be re-allocated to a new participant due to the intent-to-treat nature of the study.

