9.3 Treatment Conditions

9.3.1 HIV Usual Care (Both Arms)

All participants receive comprehensive HIV primary care, case management, addiction counseling, and social support services from HIV clinics as they would regardless of study participation. As part of protocol training, HIV clinic providers will be encouraged to offer ART within 4 weeks of randomization for participants not already prescribed ART. Current guidelines recommend offering ART to all HIV-infected participants, regardless of CD4 count (Thompson, Aberg et al. 2012). The schedule of medical care provided will be as deemed appropriate by the treating provider. HIV-infected participants are typically seen at least twice within the first month of initiating ART, and at least every 3 months thereafter for monitoring. Medical visits will not be considered study visits, though they may coincide with study visits. HIV clinic treatment will also include usual addiction counseling services, which are offered as a part of usual care in most large U.S. HIV clinics. As part of protocol training, HIV clinic providers will be asked to refer study participants to existing addiction counseling services in their clinic, as they would do regardless of study participation. Throughout the course of the trial, HIV clinics will be monitored for any potential changes that might occur in standard practice around medical management of HIV infection or addiction treatment services. HIV clinic medical and counseling visits will be tracked through medical record abstraction throughout study participation (See Section 10 Assessments).

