17.5 Analysis of secondary outcomes

The pilot study is small and thus probably under-powered for hypothesis tests. Any conclusions arising from secondary analysis must be regarded as hypothesis-generating only, and need to be validated by independent data. We contemplate no adjustment for multiplicity.

Secondary outcomes will be analyzed as indicated in the italicized text describing each secondary endpoint.

HIV outcomes:

- a) Sustained HIV RNA viral suppression (plasma HIV viral load of < 200 copies/mL) at 16 weeks (*binary, laboratory assay*). *Chi-squared test of independence of sustained viral suppression on treatment assignment.*
- b) Change in CD4 count at 16 weeks following randomization compared with baseline (*count; laboratory measurement*). T-test.

1) Engagement in HIV Care:

- a) Change in the proportion of study participants prescribed ART within 16 weeks following randomization, compared to baseline (*binary; medical record abstraction*). *Each individual can be scored either 0 (not prescribed ART) or 1 (prescribed ART) at both baseline and follow-up, after which his or her outcome score will be the follow-up score minus the baseline score. Outcome scores will be analyzed via rank-based methods such as Wilcoxon rank-sum tests. Covariates can be considered via the cumulative logit model.*
- b) Proportion of participants taking 100% of prescribed ART doses in the past 3 days at 16 weeks for those prescribed ART at any point during the 16 week trial (*proportion; self-reported ACTG adherence measure*). *Chi-squared test comparing proportion to treatment assignment, for those prescribed ART.*
- c) Number of HIV primary care visits at 16 weeks (count, chart abstraction) *outcome scores will be analyzed via rank-based methods such as Wilcoxon rank-sum tests.*

2) Substance Use:

- a) Change in 30 day opioid abstinence (by ASI-lite self-report, TLFB and urine drug screen (UDS) confirmation) in the final 30 days of the 16 week trial compared to baseline (*binary; laboratory data and self-report*). *Analysis using rank-based methods as in outcome 2a.*
- b) Change in past 30day alcohol and other drug use by ASI-lite, TLFB, and UDS at 16 weeks, compared with baseline (*binary; laboratory data and self-report*). *Analysis using rank-based methods as in outcome 2a.*

3) Participant safety, as measured by:

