17.6 ITT and Per-Protocol Analyses, Missing Data and Dropouts

Analysis will be ITT in the sense that patients will be analyzed as being members of the arm to which they were originally randomized. We plan no special adjustments for missing data.

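### Outcome visits are dated from treatment initiation, an event defined differently by arm and absent for non-initiators, and the time anchors for CD4 and retention conflict between sections

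*Protocol*

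**What the plan says.** **Visit clock.** Section 9.2.6 schedules blood and urine at 0, 1, 4, 8, 12 and "16 weeks following treatment initiation to assess participant safety, and assess the pilot study secondary aim" of change in HIV RNA and drug use. The assessment table in 10.1 labels its origin Week 0 (induction), and every later outcome visit is numbered from there.

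**Gap after randomization.** Section 9.2.8: "Participants will have up to 4 weeks following randomization to initiate his or her assigned treatment". Section 6.2 lists this as a separate phase before the 16 weeks of active treatment: "Up to 4 weeks: Detoxification and induction".

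**What counts as initiation.** In the XR-NTX arm it is the first injection (8.1). This follows detoxification where needed, a negative urine screen and, with recent opioid use, a negative naloxone challenge (9.3.3.1 and 9.3.3.2). In the TAU arm it is one dose of another medication or one day of a non-medication therapy such as a 12-step group (8.1). Anyone who has done neither by 4 weeks is an initiation failure, and no other time origin is given for them.

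**Analysis.** Section 17.6: "Analysis will be ITT in the sense that patients will be analyzed as being members of the arm" assigned at randomization. Section 9.7 follows all participants unless they withdraw or are discontinued.

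**Anchors.** CD4 in 8.2: "Change in CD4 count at 16 weeks following treatment initiation compared with screening". CD4 in 17.5: "Change in CD4 count at 16 weeks following randomization compared with baseline". Retention, a primary outcome, covers the 16 weeks after initiation in 8.1 and the 16 weeks after randomization in 17.1. ART prescription is dated from randomization throughout.

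**The concern.** A between-arm comparison in a randomized trial needs a time zero that is common to both arms and exists for everyone randomized. Initiation is neither. It happens after randomization, its prerequisites depend on the arm, and some participants never reach it.

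HIV care runs on a different clock. In both arms, "HIV clinic providers will be encouraged to offer ART within 4 weeks of randomization" to those not already prescribed it. Section 14.1 says viral suppression depends most strongly on ART use, and 6.3 says a trial with suppression as its primary outcome would need much longer than 16 weeks. Time since randomization can therefore move HIV RNA and CD4 whatever the addiction treatment does. If time to initiation differs between arms, the arms are sampled at different points on that course.

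At stake are the between-arm point estimates that 5.2 sets out to produce for planning the multi-site trial, and the completeness of outcomes for participants who are to be analysed as randomized.

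**Working it through.** **1. Reproduce the stated duration.** Inputs from 9.2: screening 1–4 weeks, detoxification and induction 0–4 weeks, active treatment 16 weeks.

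- Clock from initiation: 1 + 0 + 16 = 17 to 4 + 4 + 16 = 24 weeks. This matches the 17–24 weeks in 6.2, 9.2 and 9.7.
- Clock from randomization: 1 + 16 = 17 to 4 + 16 = 20 weeks. This does not match.

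The stated duration therefore confirms that the 16 weeks start at initiation.

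**2. Where week 16 falls.** Let d be the weeks from randomization to initiation, with d between 0 and 4 (9.2.8). The visit falls at d + 16, that is 16 to 20 weeks after randomization. The largest spread is 4 weeks, or 4/16 = 25% of the horizon.

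**3. Upper bound on the difference in ART time.** If ART starts a weeks after randomization, exposure at the week 16 visit is d + 16 − a.

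- a = 4: 12 weeks for d = 0 and 16 weeks for d = 4, ratio 16/12 = 1.33.
- a = 0: 16 and 20 weeks, ratio 20/16 = 1.25.

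Both compare the earliest possible starter with the latest. They are limits, not expected differences between arms.

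**4. Participants without a week 0.** The notes to Table 17.2.1 assume 10% attrition between recruitment and initiation: 0.10 × 50 = 5 participants. The protocol gives no split by arm. As an assumed range, 20% would be 10, 30% would be 15 and 50% would be 25 of 50.

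**5. Anchors side by side.**

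| Outcome | From initiation | From randomization | No anchor named |
|---|---|---|---|
| Treatment initiation (primary) | – | 8.1, 17.1 | – |
| Retention (primary) | 5.1, 8.1 | 17.1 | – |
| CD4 | 8.2 | 17.5 | 5.2 and 17.2 (week 16 visit) |
| HIV RNA suppression | sampling rule in 9.2.6 | – | 8.2, 17.2, 17.5 |
| ART prescription | – | 8.2, 14.1, 17.2, 17.5 | – |
| HIV primary care visits | – | – | 8.2, 17.2, 17.5 |

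**6. Retention within 17.1.** The window is 16 weeks after randomization, but the assessments are at 4, 8, 12 and 16 weeks after initiation. The last falls at d + 16. For d = 4 that is week 20, which is 20 − 16 = 4 weeks beyond the window, so one of the four assessment periods lies outside it.

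**7. What existing samples can offer.** Initiators have samples at d + 12 and d + 16 weeks after randomization. Their distances from 16 are 4 − d and d. The smaller is at most 2 weeks, reached at d = 2. Taking the nearest sample halves the worst mistiming from 4 to 2 weeks, and places samples between 14 and 18 weeks.

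**The case against.** **Direction.** A reader might infer that the longer clock belongs to XR-NTX and favours it. The document does not establish this. It gives no distribution of time to initiation by arm. Induction may take 0 weeks, detoxification applies only where needed, and the naloxone challenge applies only after recent opioid use, so an alcohol-only participant may start at once. TAU can be slow too: it may depend on an outside referral, and research staff track it weekly for up to 4 weeks. A later start is plausible for XR-NTX participants who need opioid detoxification, but no more can be said.

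**Scope.** It is tempting to say that all 16-week outcomes run from initiation. They do not: ART prescription and the 17.5 version of CD4 run from randomization. This leaves a contradiction, because no outcome visit after randomization is scheduled on that clock.

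**Non-initiators.** Nor does the protocol say that they are dropped. Section 9.7 follows them, 11.8 refers to a week 16 window, and 9.2.5 allows record abstraction up to 24 weeks after randomization, covering viral load, CD4, HIV care use and overdose. What is missing is a date. The end-of-treatment visit serves those who stop early, not those who never start.

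**Size.** Eligibility admits people already on ART and does not require unsuppressed virus, and four extra weeks may change little for a participant stable on ART. The engagement rates in the cited pilot of clinic-based buprenorphine against methadone referral cannot stand in for non-initiation here, because they concern different treatments and a different outcome.

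**Place and weight.** Choosing the sample nearest a target date is often left to a statistical analysis plan, and 17.5 calls the secondary results hypothesis-generating. Both points lower the severity. Neither cures a visit origin that the protocol itself sets, nor the two windows for a primary outcome.

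**Conclusion.** The point stands as a should-fix. Followed as written, the plan compares the arms at visits 16 to 20 weeks after randomization, leaves about 5 of 50 participants without a dated week 16 visit, and gives two conflicting anchors each for CD4 and for primary retention.

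The 5 rests on the protocol's 10% planning assumption. The 25% (horizon) and 33% (ART time) figures are upper bounds that need extreme start times. The average timing difference between arms, its sign and its effect on the estimates cannot be determined from the document, so no bias in favour of either arm is asserted. Restricting retention to initiators is a stated choice and is not disputed. No sample-size or precision figure depends on this point.

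**What to change.** 1. Date the between-arm secondary outcomes (HIV RNA, CD4, substance use, ART, HIV visits, overdose and Concise Health Risk Tracking) from randomization for all randomized participants. Use the scheduled sample or visit nearest 16 weeks after randomization, supplemented by the record abstraction that already runs to 24 weeks.
2. State that participants who do not initiate attend visits dated from randomization.
3. Keep the initiation clock for injections, dose counts, retention among initiators and the week 1 safety visit.
4. Name one anchor per outcome and use it in 8.1, 8.2, 9.2.6, 17.1 and 17.5. For retention, make the 17.1 window agree with its own assessment times.

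**Cost.** Mostly wording and visit windows. HIV RNA, urine screens and the Timeline Follow Back are already collected at weeks 4, 8, 12 and 16, and CD4 at weeks 12 and 16. The ASI-Lite is planned only at baseline and week 16 or end of treatment, so it would have to move to, or be added at, the visit used for late starters. Nearest-sample selection leaves up to 2 weeks of mistiming; a visit set at exactly 16 weeks after randomization would remove it, at the price of an extra visit for some. For late starters, the outcome would reflect up to 4 fewer weeks on treatment than now.

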9.2.7 Baseline Assessment

After the enrollment process is complete, study staff will prepare a new data record for the participant and the baseline assessments will be administered through a computer assisted data collection instrument. Each assessment question is displayed on a computer monitor, allowing the interviewer to read the questions and then enter the participants' responses directly into the computer. The baseline assessments are detailed in Section 10.0 and capture participant medical, psychiatric, and drug use history, HIV status and care, quality of life and current health status. The baseline assessment will take approximately 45 - 60 minutes to complete.

9.2.8 Randomization

We anticipate that the timing of randomization will be variable, but follow shortly after baseline assessments and final confirmation of eligibility. Participants will have up to 4 weeks following randomization to initiate his or her assigned treatment. Success in initiating assigned treatment will be tracked.

Participants will be randomized in a 1:1 fashion to either office-based XR-NTX or TAU using a permuted block design with randomly-sized blocks. Predominance of alcohol vs. opioid use disorder for a given participant will

likely be strongly correlated with primary and secondary outcomes, and this variable will be recorded upon randomization. The severity of opioid and alcohol use disorder will also likely be an important independent predictor of treatment retention and substance use (Sullivan, Rothenberg et al. 2006; Carpenter, Jiang et al. 2009; Brooks, Comer et al. 2010). Participants need not be abstinent from opioids or alcohol at the time of randomization.

The randomization procedure will be conducted in a centralized process through the Data and Statistical Center (DSC). Specifically, randomization schedules will be created by the study statistician for each site. The randomization schedules will be of a randomized-block nature to ensure relative equality of assignment across condition across the recruitment period and to prevent the potential for study staff guessing the next assignment which is heightened when a fixed block-size is used. After the baseline assessment is successfully completed, a designated study staff member will perform the randomization. Randomization for each participant is done over the Internet using the Enrollment Module in AdvantageEDC.

The DSC statistician will review the randomization data on a regular basis to ensure that the scheme is being implemented according to plan. If a participant drops out of the study at any point after randomization, the randomization slot will not be re-allocated to a new participant due to the intent-to-treat nature of the study.

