The pilot study consists of a two-arm, 16-week, open-label, randomized, pilot trial of XR-NTX vs. TAU for treatment of opioid and alcohol use disorders in HIV-infected patients. Study participants are individuals with HIV infection and alcohol and/or opioid use disorders and who have received patient-centered information about both antagonist and agonist treatment options for alcohol and opioid use disorders. During screening, eligible participants will be surveyed regarding their attitudes about opioid antagonist therapy for opioid and alcohol use disorders (Aim 2). We will track the rate of participant recruitment (i.e., no more than 50 participants over no more than 12 months) to estimate duration of study recruitment required for a multisite study (Aim 3). Eligible patients are randomized in a 1:1 ratio to receive XR-NTX vs. TAU (Aim 4). Participants with both alcohol and opioid use disorders will be categorized by their self-reported substance of choice. XR-NTX (provided as Vivitrol®) will be administered by HIV clinic providers as a monthly intramuscular injection. Study visits will occur every 4 weeks for collection of blood and urine samples, safety, and other assessments. Primary outcomes of treatment initiation within 4 weeks of randomization, and retention at 16 weeks (maximum of 4 XR-NTX injections) and analyzed by intent-to-treat will be assessed. Secondary outcomes assessed at 16 weeks include change in 1) HIV-1 RNA viral suppression, 2) illicit drug and alcohol use, 3) HIV care engagement (receipt of ART, HIV visit adherence, ART adherence), and safety (percent with precipitated withdrawal, overdose, transaminitis).

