9.3.4 Treatment as Usual (TAU)

Participants assigned to the TAU group will receive the standard treatment for alcohol and opioid use disorders provided at each HIV clinic. The standard of care in U.S. and Canadian HIV clinics is currently to link with opioid agonist treatment services. Opioid substitution therapy is recommended for HIV-infected participants with opioid dependence (Thompson, Aberg et al. 2012; Thompson, Mugavero et al. 2012), and many HIV practices are being encouraged to adopt clinic-based BUP/NX (HIV/AIDS Bureau Special Projects of National Significance Program 2012). The standard of care for treatment of alcohol use disorders in HIV clinics is referral to detoxification, if needed, as well as outpatient or inpatient rehabilitation programs and 12-step groups, and/or on-site substance abuse counseling services. Medication-assisted treatment of alcohol use disorders with naltrexone, disulfiram, or acamprosate is rare in HIV clinics.

Many HIV clinics receive funding from the Ryan White Care Act for case management and addiction/mental health counseling services to facilitate engagement of HIV-infected patients with substance use disorders in treatment. In a 6-month randomized trial of methadone maintenance referral strategies, passive referral of heroin users resulted in 8% methadone maintenance enrollment at 6 months vs. 29% enrollment among those randomized to case-management assisted referrals ($p = .006$) (Coviello, Zanis et al. 2006).

Methadone maintenance referrals in HIV clinics may more closely approximate case-managed referral enrollment due to the presence of Ryan White Care Act-funded case managers and counselors.

During the formal site selection process, a thorough assessment will be conducted of each site's standard practice for linkage to addiction treatment services. Throughout the course of the trial, HIV clinics will be monitored for any potential changes that might occur in standard practice around linking HIV-infected clinic patients to substance use treatment.

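### The between-arm tests fixed in Section 17.5 use neither site, within which randomization is blocked, nor the recorded primary substance; the cost is precision, not bias

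*Protocol*

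**What the plan says.** On allocation, Protocol Section 9.2.8 says: "Participants will be randomized in a 1:1 fashion to either office-based XR-NTX or TAU using a permuted block design with randomly-sized blocks". It adds that "randomization schedules will be created by the study statistician for each site". Section 7.5 fixes two sites.

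On the comparator, Section 9.3.4 says that TAU participants "will receive the standard treatment for alcohol and opioid use disorders provided at each HIV clinic".

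On primary substance, Section 9.2.8 says that predominance of alcohol or opioid use disorder will "likely be strongly correlated with primary and secondary outcomes, and this variable will be recorded upon randomization". Section 6.1 defines the category for people with both disorders: "Participants with both alcohol and opioid use disorders will be categorized by their self-reported substance of choice". It is not named as a stratification factor.

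On analysis:
- Section 17.3 estimates initiation (Aim 4A) and retention (Aim 4B) separately in each arm with exact binomial intervals. It specifies no between-arm test or interval.
- Section 17.5 names a method for nearly every secondary outcome. For viral suppression it is "Chi-squared test of independence of sustained viral suppression on treatment assignment". CD4 change gets a t-test. ART prescription, HIV visits and the substance-use outcomes get rank-based tests. Overdose gets a chi-squared test or logistic regression. Liver enzymes and the Concise Health Risk Tracking score get a paired t-test or least squares.
- Unnamed covariates may be considered through a cumulative logit model for ART prescription.

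Section 17.5 mentions neither site nor primary substance.

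**The concern.** Blocking within site makes the arms nearly equal at each site. An analysis that ignores site keeps the between-site variation in its error term although the design has removed that variation from the arm difference. If outcome rates differ by site, the standard error is then larger than the design warrants and the test tends to be conservative. A site difference is plausible here because the comparator depends on the clinic.

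Primary substance is a separate matter. The randomization does not balance it, so with about 25 per arm it can be unequal by chance. The protocol expects it to be strongly prognostic and records it, then fixes tests that mostly cannot use it.

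At stake are the between-arm estimates that Aim 4 is meant to hand to a later multi-site trial. Where adjustment is permitted, no covariate is named, so the choice could be made after the data are seen.

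**Working it through.** **1. The plan's own precision figures.** Inputs from Table 17.2.1: 2.28 participants per site-month, 2 sites, 12 months, cap of 50, and 10% attrition before initiation.
- Expected uncapped recruitment: 2 × 12 × 2.28 = 54.72. The 20th percentile of min(50, Poisson(54.72)) is 48; the table says 48.
- Largest exact 95% half-width for initiation: 0.209 at 24 per arm; the table says 0.21.
- For retention, with 21 to 22 per arm after attrition: 0.223 and 0.218; the table says 0.22.

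These figures reproduce. They are per-arm intervals, so stratifying the arm comparison changes none of them.

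**2. Leaving out site: standard error of the arm difference.** The protocol gives no site-specific rates, so the rates *a* and *b* are assumptions, shown as a range. Sites are taken as equal in size.
- Unstratified unit variance: *m*(1 − *m*), with *m* = (*a* + *b*)/2.
- Within-site unit variance: [*a*(1 − *a*) + *b*(1 − *b*)]/2.
- SE ratio: the square root of within-site over unstratified variance.

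| Assumed site rates | Unstratified | Within-site | SE ratio |
|---|---|---|---|
| 50% / 70% | 0.2400 | 0.2300 | 0.98 |
| 40% / 80% | 0.2400 | 0.2000 | 0.91 |
| 30% / 80% | 0.2475 | 0.1850 | 0.86 |

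At 40%/80% with 25 per arm, the standard error is √(2 × 0.24/25) = 0.139 unstratified and √(2 × 0.20/25) = 0.126 stratified. The unstratified variance is 0.24/0.20 = 1.20 times the stratified one.

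**3. Leaving out site: test behaviour.** Simulation with 20,000 trials per scenario, 25 participants per site, permuted blocks within site (assumed sizes 2 and 4) and two-sided 5% level. The chi-squared test without continuity correction is compared with the Cochran-Mantel-Haenszel (CMH) test stratified by site. Power is for a 30-point arm difference. The site effects are none, moderate (20 points) and strong (50 points).

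| Site effect | Type I error, chi-squared | Type I error, CMH | Power, chi-squared | Power, CMH |
|---|---|---|---|---|
| None | 6.2% | 5.2% | 64% | 62% |
| Moderate | 5.9% | 5.3% | 64% | 64% |
| Strong | 3.2% | 4.7% | 64% | 72% |

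The unstratified test is clearly conservative only with the strong site effect, where it gives up about 8 points of power. With no site effect, stratifying costs about 2 points. Some of that gap may reflect the chi-squared test running above its nominal 5% at this sample size.

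**4. Leaving out primary substance.** Treat the number with alcohol predominance in each arm as independent binomials with *n* = 25. The chance that the arms differ by at least 5 participants (5/25 = 20 points) is 20% for an assumed alcohol share of 50%, 19% for 60% and 16% for 70%. If the outcome differs by an assumed 40 points between substances, such an imbalance shifts the unadjusted arm difference by 0.20 × 0.40 = 0.08, or 8 points.

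**The case against.** The case for leaving the plan alone has real substance.

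- **Scope.** A reader might infer that no analysis uses site. Section 17.3 contradicts that: the Aim 3 recruitment bootstrap resamples sites and draws inter-arrival times within site.
- **Primary outcomes.** A reader might infer that the intervals for Aims 4A and 4B are too wide. Section 17.3 specifies only per-arm exact intervals, which are reasonable for the mixed population. No between-arm interval is specified that could be too wide, even though Objectives 4A and 4B in Section 5.1 are worded as comparisons.
- **Bias.** A reader might infer a biased comparison. Blocked 1:1 allocation within site rules that out for site.
- **Primary substance.** A reader might apply the 20% variance overstatement to primary substance as well. It does not apply. Substance is not a stratification factor, so the pooled variance is correct for the unadjusted difference and the interval is valid.
- **Status and size.** Section 17.5 calls the secondary results hypothesis-generating, and the study has at most 50 participants. At the lower recruitment rate in Table 17.2.1, two sites would yield about 22 at the 20th percentile. Strata would then be sparse, especially for overdose. Section 7.7 also tries to limit site variability through site selection.

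All of this stands and sets the size of the point. One further argument, that strata and covariates belong in a statistical analysis plan that is not shown, carries less weight. Section 17.5 is not silent: it fixes tests outcome by outcome, and the optional adjustment it allows for some of them names no covariate.

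**Conclusion.** The point holds at low severity. The between-arm tests fixed in Section 17.5 leave out the factor within which randomization is blocked, and a recorded baseline variable that the protocol says will "likely be strongly correlated with primary and secondary outcomes".

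For site, the consequence is lost precision and no bias. The standard error would be 2% to 14% smaller with stratification across the assumed site differences, and about the same if sites do not differ. These figures rest on assumed site rates and two equal sites.

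For primary substance, the unadjusted analysis is valid but forgoes precision and leaves chance imbalance uncorrected. An 8-point shift is possible under the assumed 20-point imbalance and 40-point prognostic difference.

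No figure stated in the protocol changes.

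**What to change.** In Section 17.5:
- Stratify the between-arm comparisons by site: the CMH test or a Mantel-Haenszel risk difference for binary outcomes, a stratified rank-sum test for ranked outcomes, and a site term in linear models.
- Name primary substance (alcohol or opioid) as a prespecified covariate where event counts allow.
- Keep simple unadjusted or exact methods for rare outcomes such as overdose.

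In Section 17.3, keep the per-arm exact intervals. If a between-arm difference for Aim 4A or 4B is reported, stratify it by site.

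Show arm results by site and by primary substance descriptively.

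The cost is analysis wording only, since both variables are already known for each participant. The downside is about 2 points of power if site has no effect, and sparse strata if recruitment is low.
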